4.3 Duration of Therapy

Nivolumab will be dosed per standard of care approved guidelines. Nivolumab administration will be repeated, at the discretion of the treating medical oncologist until [5]:

- Disease progression as per the ir-RECIST criteria
- Inter-current illness that prevents further administration of treatment
- Unacceptable adverse event(s)
- Subject decides to withdraw from the study, **OR**
- General or specific changes in the patient's condition render the subject unacceptable for further treatment in the judgment of the principal investigator or medical oncologist.

SABR will be performed after the second Nivolumab dose but before the fourth dose (i.e. before the second Nivolumab cycles).

4.4 Duration of Follow Up

For patients who respond to treatment, subjects will be followed for five years or until death (although findings will be analyzed and reported at a median follow up of 2-4 years), whichever occurs first. For these patients, follow-up will be every 8 - 12 weeks from study registration with imaging studies and physical exam (recommended) every 8-12 weeks for the first year, then every 8-12 weeks for the second year, then every four-six months thereafter for a total of five years.

Subjects who show progressive disease will be followed for survival and will no longer strictly adhere to study calendar requirements.

Subjects removed from treatment for unacceptable adverse events will be followed until resolution or stabilization of the adverse event.

4.5 Removal of Subjects from Protocol Therapy

Subjects will be removed from therapy when any of the criteria listed in Section 5.5 apply, however will continue to be followed up as per protocol described above. Study coordinators will notify the Principal Investigator, and document the reason for study removal and the date the subject was removed in the Case Report Form.

5.0 STUDY PROCEDURES

5.1 Screening/Baseline Procedures

Assessments performed strictly for research purposes will be done only after obtaining informed consent. Assessments performed for clinical indications (not exclusively for research purposes) may be used for baseline values even if the studies were done before informed consent was obtained.

All screening procedures must be performed within 8 weeks prior to registration unless otherwise stated. If patients remain eligible after the screening occurs, they will be registered. The screening procedures include:

5.1.1 Informed Consent

5.1.2 Medical history

Complete medical and surgical history, history of infections and pulmonary risk factors

5.1.3 Demographics

Age, gender, race, ethnicity

5.1.4 Review subject eligibility criteria

5.1.5 Review previous and concomitant medications

5.1.6 Physical exam (recommended) including vital signs, height and weight

Vital signs (temperature, pulse, respirations, blood pressure, O2 saturation), height, weight: should be done at screening and prior to first dose of Nivolumab

5.1.7 Performance status

Performance status evaluated prior to study entry according to Appendix A.

5.1.8 Adverse event assessment

Baseline adverse events will be assessed. See section 7 for Adverse Event monitoring and reporting.

5.1.9 Hematology (within 14 days of registration)

Recommended

5.1.10 Blood draw for correlative studies

Must be done 0-28 days prior to first dose. See Section 9.0 for details.

5.1.11 Serum/urine chemistries (within 14 days of registration)

Recommended

5.1.12 Pregnancy test (for females of child bearing potential)

Per standard of care at the discretion of the treating medical oncologist.

5.1.13 Radiographic Imaging

5.1.13.1 CT chest, abdomen and pelvis (recommended with IV contrast) must be done within 6 weeks of registration. MRI can replace CT at the discretion of the treating physician.

5.1.13.2 Brain MRI is allowed up to 3 months prior to registration.

5.1.14 Biopsy of metastatic lesion

5.1.14.1 Pre-treatment biopsy:

A CT-guided biopsy of a tumor lesion will be performed prior to study registration, unless previous biopsy of metastatic site exists in which case a pretreatment biopsy is not required.

5.1.14.2 Post-treatment elective biopsy:

An elective post-treatment biopsy will be performed at 8 weeks (+/- 2 weeks, >4weeks after SABR) (first follow up visit) and for this biopsy, any site other than a lymph node and a treated site is acceptable. In case of CR no lesions may remain to be biopsied.

5.1.15 QoL Questionnaires

FACT-G, EQ-5D, FKSI, Cost Effectiveness questionnaire: These forms will be referred to collectively as QoL Questionnaires and will be collected prior to first Nivolumab dose and at specific time-points as indicated in section 5.4

5.1.16 Tumor assessment

To be performed on CT or MRI from 5.1.13.

5.2 Procedures During Treatment

SABR treatment requires one week for planning and one week for delivery of the 1 or 3 fractionation schemes. Thus, CT simulation and treatment planning will take place any time before the radiation. SABR will be performed after 1st cycle of Nivolumab infusion. Vital Signs, AE Assessment, Medication Review and Laboratory Review may be performed by a Nurse or Physician.

5.2.1 Prior to first Nivolumab dose (0-28 days prior)

- Focused physical exam (recommended)
- Vital Signs
- Performance Status (recommended)
- AE Assessment
-
- For WOCBP, pregnancy test within 24 hours of first dose of Nivolumab
- Blood draws for immunologic studies
- FACT-G, EQ-5D, FKSI, Cost-Assessment questionnaires

5.2.2 Day 1 of Nivolumab cycle

- Focused PE (recommended)
-
- All labs (except corollary blood collections) will be done per standard of care at the discretion of treating medical oncologist.
- First Nivolumab infusion cycle administered
- Blood draws for immunologic studies at baseline, follow up q 8-12 weeks (until discontinued or within first year of enrollment, whichever is first) and at 1 year (if discontinued before 1 year).

5.2.3 Pre-RT

- CT simulation for SABR planning
-

5.2.4 Radiation Treatment

- AE assessment
- Vital Signs
- SABR treatments will be performed after 1st cycle of Nivolumab infusion.

These cycles will continue (without SABR) until patient is discontinued from Nivolumab as discussed above.

5.3 Follow-up Procedures

- For patients who are still receiving Nivolumab:

Subject will be followed every 8-12 weeks starting from the date of registration for the first two years. , then every four-six months thereafter for five years or death, whichever comes first. The following procedures will be performed at each follow up:

- Physical exam (recommended), Performance Status (recommended), Vital Signs, Medication Review, AE assessment
- HR-QoL questionnaire at baseline, and then at six month intervals until patient meets primary endpoint
- Blood collection for correlative immunologic studies (see section 9.0): In total, all patients will get blood draws for correlative studies at baseline, follow up q 8-12 weeks (until discontinued or within first year of enrollment, whichever is first) and at 1 year (if discontinued before 1 year).
- Radiographic imaging: Tumor assessments will be completed by the investigator using the RECIST and ir-RECIST criteria as above.
 - CT chest, abdomen and pelvis with IV contrast (contrast recommended), if allowable by renal function. MRI with contrast (contrast recommended) can replace CT.
 - MRI, if necessary to confirm CT findings, at the discretion of physician

- For patients who have been discontinued from Nivolumab (See Section 4.3): Subject will be followed within 3 months from last dose ((+/- 2 months), or may be on date of discontinuation).

The following procedures will be performed:

- Physical exam (recommended), Performance Status (recommended), Vital Signs, Medication Review, AE sssessment
- Subsequent anti-cancer treatment/s
- Blood samples for correlation immunologic studies

After that, survival visits/phone calls continue annually to include Survival Status, AE Assessment, and Subsequent anti-cancer treatment/s.

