7.3.1 Definitions

An adverse event is defined as any untoward or unfavorable medical occurrence in a human research study participant, including any abnormal sign (for example, abnormal physical exam, imaging finding or clinically significant laboratory finding), symptom, clinical event, or disease, temporarily associated with the subject's participation in the research, whether or not it is considered related to the subject's participation in the research.

Adverse events encompass clinical, physical and psychological harms. Adverse events occur most commonly in the context of biomedical research, although on occasion, they can occur in the context of social and behavioral research. Adverse events may be expected or unexpected.

Acute Adverse Events

An adverse event is defined as any untoward or unfavorable medical occurrence in a human research study participant, including any abnormal sign (for example, abnormal physical exam or laboratory finding), symptom, clinical event, or disease, temporarily associated with the subject's participation in the research, whether or not it is considered related to the subject's participation in the research. Adverse events occurring through the time period of **the start of treatment through the first follow up occurring 12 weeks post treatment** will be considered acute adverse events. All acute adverse events will be assessed and reported as per below.

Late Adverse Events

Adverse effects occurring in the time period from the **end of acute monitoring**, to 3 years post treatment for progression or death (whichever comes first), will be defined as late adverse events. These events will include all adverse events reported directly to a member of the study team and will be captured, assessed, graded and reported as appropriate.

In addition, the study team will review encounters in a select specialty category relevant to study endpoints. These select specialties include hospitalizations, medical oncology, and radiation oncology records and will be limited in scope based on categorization of events (**GU/GI**) and also the type of records that will be queried (hospitalizations, **medical oncology, and radiation oncology**).

Adverse events encompass clinical, physical and psychological harms. Adverse events occur most commonly in the context of biomedical research, although on occasion, they can occur in the context of social and behavioral research. Adverse events may be expected or unexpected.

Severity

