7.6 Steps to Determine If an Adverse Event Requires Expedited Reporting

Step 1: Identify the type of adverse event using the NCI Common Terminology Criteria for Adverse Events (CTCAE v4).

Step 2: Grade the adverse event using the NCI CTCAE v4.

Step 3: Determine whether the adverse event is related to the protocol therapy Attribution categories are as follows:

- Definite – The AE *is clearly related* to the study treatment.
- Probable – The AE *is likely related* to the study treatment.
- Possible – The AE *may be related* to the study treatment.
- Unlikely-The AE may NOT be related to the study treatment.
- Unrelated – The AE *is clearly NOT related* to the study treatment.

Note: This includes all events that occur within 30 days of the last dose of protocol treatment. Any event that occurs more than 30 days after the last dose of treatment and is attributed (possibly, probably, or definitely) to the agent(s) must also be reported accordingly.

Step 4: Determine the prior experience of the adverse event.

Expected events are those that have been previously identified as resulting from administration of the agent. An adverse event is considered unexpected, for expedited reporting purposes only, when either the type of event or the severity of the event is not listed in:

- the current known adverse events listed in the Agent Information Section of this protocol;
- the drug package insert (if applicable);
- the current Investigator's Brochure (if applicable);
- the Study Agent(s)/Therapy(ies) Background and Associated Known Toxicities section of this protocol.

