7.7 Reporting Requirements for Adverse Events

7.7.1 Expedited Reporting

- The Principal Investigator must be notified within 24 hours of learning of any serious adverse events, regardless of attribution, occurring during the study or within 30 days of the last administration of the study drug.
- If necessary, suspected adverse reactions will also be reported to FDA at [name] or www.fda.gov/medwatch.

- The IRB must be notified within 10 business days of “any unanticipated problems involving risk to subjects or others” (UPR/UPIRSO).

The following events meet the definition of UPR:

1. Any serious event (injuries, side effects, deaths or other problems), which in the opinion of the Principal Investigator was unanticipated, involved risk to subjects or others, and was possibly related to the research procedures.
 2. Any serious accidental or unintentional change to the IRB-approved protocol that alters the level of risk.
 3. Any deviation from the protocol taken without prior IRB review to eliminate apparent immediate hazard to a research subject.
 4. Any new information (e.g., publication, safety monitoring report, and updated sponsor safety report), interim result or other finding that indicates an unexpected change to the risk/benefit ratio for the research.
 5. Any breach in confidentiality that may involve risk to the subject or others.
 6. Any complaint of a subject that indicates an unanticipated risk or that cannot be resolved by the Principal Investigator.
- The FDA should be notified within 7 business days of any unexpected fatal or life-threatening adverse event with possible relationship to study drug, and 15 business days of any event that is considered: 1) serious, 2) unexpected, and 3) at least possibly related to study participation.

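### Section 5.3 lets the only near-term adverse-event assessment after nivolumab stops fall on the day of discontinuation, with the next scheduled contact about a year later, so the protocol's 30-day window and possibly its 12-week window need have no timely scheduled assessment

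*Combined protocol and SAP*

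**What the plan says.** Section 5.3 has two branches. Patients still on nivolumab are seen every 8-12 weeks for two years and less often after that. For those who have stopped, it says: "Subject will be followed within 3 months from last dose ((+/- 2 months), or may be on date of discontinuation". That visit covers AE assessment, medication review, subsequent anti-cancer treatment and a blood sample. The text continues: "After that, survival visits/phone calls continue annually to include Survival Status, AE Assessment, and Subsequent anti-cancer treatment/s".

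The safety sections use windows that run past the last dose:

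- Section 7.6, on which events to consider for expedited reporting: "This includes all events that occur within 30 days of the last dose of protocol treatment". Later events count if attributed to the agent.
- Section 7.7.1, on serious events to be notified to the principal investigator: "regardless of attribution, occurring during the study or within 30 days of the last administration of the study drug".
- Section 7.3.1, on the acute period: "the start of treatment through the first follow up occurring 12 weeks post treatment". Late events are captured as follows: "These events will include all adverse events reported directly to a member of the study team". A review of selected records, limited to GU/GI categories, is added.

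Other follow-up rules are in 4.4 and 5.4. Responders are followed every 8-12 weeks in years 1 and 2, with no condition that they stay on the drug. Patients with progression are followed for survival and released from the strict calendar. Patients removed for toxicity are followed until that event settles. The 5.4 table sends everyone other than responders to 5.3.

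**The concern.** An assessment made on the day a patient stops can record only what has happened by then. Where that day is close to the last dose, it says little or nothing about the 30 days that 7.6 and 7.7.1 count, or about a 12-week acute period running from the last dose. The follow-up visit that 7.3.1 presumes at 12 weeks is not scheduled for these patients anywhere in 5.3. The subsequent-treatment item has the same weakness: on the day of stopping there will often be nothing to record.

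Toxicity is a secondary objective (2.2.7), and 11.3 plans an exact binomial toxicity rate with a 95% confidence interval. Section 1.4.2 concedes that little is known about the side effects of the combination. An event that begins after stopping and is not ascertained can only lower the count.

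**Working it through.** The plan states no figure on this point to reproduce. The check is calendar arithmetic on its own windows.

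**Inputs.** Near-term visit: 3 months +/- 2 months after the last dose, or the date of discontinuation (5.3). Later contact: annual (5.3). Windows: 30 days (7.6, 7.7.1) and 12 weeks = 12 x 7 = 84 days (7.3.1).

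**Conventions.** Day 0 is the last nivolumab dose, a month is 30.4 days, the annual contact is counted from the near-term visit, and the 12-week window is taken to run from the last nivolumab dose.

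**Step 1: the written window.** 3 - 2 = 1 month and 3 + 2 = 5 months, or about day 30 to day 152.

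**Step 2: each case against the two windows.**

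| Near-term AE assessment | First scheduled look-back over all of days 1-30 | First scheduled look-back over all of days 1-84 |
|---|---|---|
| Day 0 (discontinuation option) | about day 365, i.e. 365 - 30 = 335 days after the window closes | about day 365, i.e. 365 - 84 = 281 days after it closes |
| Day 30 (early edge) | day 30, as the window closes | about day 30 + 365 = 395, i.e. 395 - 84 = 311 days after it closes |
| Day 152 (late edge) | day 152, i.e. 152 - 30 = 122 days after it closes | day 152, i.e. 152 - 84 = 68 days after it closes |

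The written window therefore always covers the 30 days in retrospect. It covers 12 weeks only if the visit is at day 84 or later. The discontinuation option, when used at day 0, covers neither.

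**Step 3: discontinuation declared after the last dose.** If the lag is L days, a visit on the date of discontinuation leaves max(0, 30 - L) days of the first window and max(0, 84 - L) days of the second unassessed. The documents give no typical L, so a range is shown:

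- L = 0: 30 and 84 days.
- L = 21 (an assumption, using the three-week interval that 1.4.2 quotes for the earlier trials): 9 and 63 days.
- L = 42 (the six-week delay beyond which 4.2.1 requires discontinuation, with exceptions): 0 and 42 days.

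**Step 4: do the other routes find new events?**

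- Investigator notification in 7.7.1 starts when someone learns of a serious event. It does not look for one.
- The record review in 7.3.1 belongs to the late period and is limited to GU/GI. The nivolumab experience in 7.2.4 includes pneumonitis and endocrine events.
- Section 4.4 and the AE monitoring text follow events that already exist.
- The annual contact does ask about AEs, but over as much as a year of recall.

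**Step 5: weight of one event.** One missed patient with an event moves the toxicity rate by 1/21 = 4.8 or 1/19 = 5.3 percentage points.

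**Step 6: exposure after stopping.** Section 3.1.9 equates 90 days plus five half-lives to 31 weeks. 31 x 7 = 217 days, and 217 - 90 = 127 days for five half-lives. On the protocol's own figures, exposure continues well beyond a day-0 visit.

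**The case against.** The strongest reply is that the plan has several other ways to learn of these events, and that the discontinuation-day visit is an option rather than the rule. The annual contacts include AE assessment, serious events go to the investigator once known, attributed events beyond 30 days are reportable, and some records are reviewed. This stands against any claim that post-treatment toxicity goes unobserved. It does not supply a timely scheduled assessment.

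Several stronger readings are tempting, and the documents do not support them:

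- **That nearly every patient is affected.** Responders have 8-12-weekly follow-up under 4.4 and 5.4 whether or not they remain on nivolumab, although this conflicts with 5.3 once they stop. The quoted median PFS of 4-4.6 months is not time on treatment, since treatment beyond progression is allowed.
- **That observation after the last dose is always zero.** As Step 3 shows, discontinuation may be declared weeks later.
- **That the six-patient safety look fails.** Section 11.2 gives it its own point at 8 weeks after registration, and the comparison with nivolumab alone in 7.8 is confined to those six.
- **That patients who stop early are the most prone to further toxicity.** Nothing in the documents says so, and those removed for toxicity are followed until the event settles.
- **That community administration leaves events unseen.** Section 4.2.1 allows it only if the treating study oncologist takes on reporting and follow-up.

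It is also fair to say that 7.6 and 7.7.1 set reporting scope rather than visit dates, and that 7.3.1 does not say whether its 12 weeks run from SABR or from nivolumab. If SABR is meant, many patients would pass that window while still on the 8-12-weekly schedule. What remains is the 30-day gap, and the 12-week gap on the nivolumab reading.

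**Conclusion.** The point holds as a mismatch between the visit schedule in 5.3 and the AE windows in Section 7. When the option is used at or near the last dose, the next scheduled assessment able to look back over the 30-day window comes about 335 days after that window closes. For a 12-week window counted from nivolumab, the figure is about 281 days. The mismatch is clearest for patients who stop for progression.

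Under-ascertainment of the toxicity rate is possible, and its direction is downward, but its size is unknown. It depends on how often sites use the option, on the lag between last dose and discontinuation, and on how much passive reporting recovers. A reader might infer a demonstrated bias against nivolumab alone; the documents give no estimate of one, and 11.3 plans no full-cohort toxicity comparison. The response-rate endpoint is not touched. The change is worth making because it costs so little.

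Assumptions: 5.3 means 3 months plus or minus 2, and the annual contact is counted from the near-term visit.

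**What to change.** 1. In 5.3, keep the examination and blood draw on the date of discontinuation where convenient. Require the AE and subsequent-treatment assessment, by phone if preferred, at least 30 days after the last nivolumab dose and within the 1-5 months already written.
2. In 7.3.1, state whether *post treatment* means after SABR or after the last nivolumab dose. If nivolumab, time that contact at 12 weeks or later (about day 84 to day 152), so that one contact covers both windows.
3. Reconcile 4.4, 5.3, 5.4, 7.3.1, 7.6 and 7.7.1, including which schedule applies to a responder who has stopped the drug.

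The cost is at most one extra phone call per patient, so no more than 21 calls, plus amendment wording. No new visit type, test or change to treatment is involved.

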5.4 Time and Events Table

The above recommended labs are listed in the following table but investigators in the various participating institutions may obtain labs per their standard of care to assess suitability for treatment.

	Pre-study	Cycle Day 1 Infusion	Pre-RT	Radiation Treatment	Follow Up Schedule for Patients who respond to treatment (for other patients refer to Section 5.3)		
					Months 1-12: q8-12 Weeks	Months 13-24: q8-12 Weeks	Months 25-60: q16-24 Weeks
Informed Consent	X						
Vital Signs	X	X		X	X	X	X
Medical History	X				X	X	X
Physical Exam (recommended)	X	X			X	X	X
Performance Status (recommended)	X				X	X	X
AE Assessment	X	X		X	X	X	X

Medication Review		X				X	X	X
CT Chest, Abd**, pelvis w/ Contrast	X					X	X	X
MRI Brain w/contrast	X							
Tumor Assessment	X							
Biopsy of metastatic lesion	X^					X@		
CT Simulation			X					
SABR Treatment				X				
Blood Draw for Correlative Studies (Section 9.0)	X#	X#		X#		X#		
QOL Questionnaires	X					X%	X%	X%
Cost-Effectiveness Questionnaire	X					X^^		
Tumor assessment	X							

** MRI should be considered, in place of CT, on an individual basis if felt to be better by the radiation or medical oncologist.

¹ For cycle 1, no need to repeat blood tests at day 1

Immunologic blood collection is needed at baseline, follow up q 8-12 weeks (until discontinued or within first year of enrollment, whichever is first) and at 1 year (if discontinued before 1 year).

^ if previous biopsy of metastatic site with adequate review of slides is not available.

^^ Cost Effectiveness Questionnaire administered at Baseline, 8 week follow up and 6 month follow up.

@ Biopsy is optional at 8 weeks

% QoLs will be done at baseline and then at 6 month intervals

